Despite the established role of emergency departments (EDs) in developed countries, most of the world’s population does not have access to timely and effective emergency care. This situation is slowly being addressed as the global health community recognises the value of EC systems.⁴

Little is known about the prevalence of triage in low- and middle-income countries (LMICs), including in the Pacific region. There is also limited evidence about the utility, validity and reliability of triage scales in these contexts.⁵ While a landmark study in a paediatric ED in Malawi demonstrated that training staff in emergency skills, introducing triage and improving flow, substantially reduced case fatality rates, the mortality reduction attributable to triage is unknown.⁶

A small number of triage scales have been developed for resource-limited (RL) environments. The most widely studied is the four-tier South African Triage Scale (SATS), which has demonstrated reasonable reliability and validity.⁵ A recent systematic review of adult triage scales in LMICs found that the evidence supporting any particular triage scale was moderate at best.⁵

In the Pacific region, SATS has provided a foundation for the three-tier Solomon Islands Triage Scale (SITS), which has recently been piloted in Honiara.⁷ The World Health Organization (WHO) is also preparing to release a three-tier triage scale [personal communication, [name]]. Neither of these instruments has been prospectively validated.

Although the potential value of triage systems in resource-limited EDs is increasingly recognised, the current evidence base is limited. The impact on process indicators (eg, time to assessment) and clinical outcomes (eg, mortality) for time-critical conditions is largely unknown.

Evaluating triage systems

One of the challenges in evaluating and comparing triage systems is a lack of consistent methodology. Most studies have focussed on reliability and validity as markers of performance.

Reliability is an essential component of a triage system, and refers to the degree to which repeated assessments of the same patient will deliver the same category of urgency.⁸ This is typically assessed using inter-rater agreement.

The validity of a triage system refers to its ability to reflect the true urgency of the patient's condition. A major challenge in validity assessment is the absence of a definitive or 'gold standard' measure of urgency.² A range of surrogate markers have therefore been used to assess criterion and predictive validity, namely ED outcomes such as admission rate, mortality and length of stay. Some authors have suggested that a Delphi approach might also be useful for the evaluation of triage systems in developing settings.⁸

Several studies have calculated under- and over-triage rates as a measure of validity.⁹⁻¹² These typically use acceptable limits defined by the American College of Surgeons Committee on Trauma (ACS COT) as a reference standard.¹³

Emergency care and triage in Papua New Guinea

Papua New Guinea (PNG), a Pacific Island Country (PIC) with a population of approximately 8 million, is faced by significant challenges in healthcare delivery. These include under-resourcing, a limited health workforce, a high burden of communicable disease (including significant rates of HIV/AIDS and tuberculosis) as well as an increasing prevalence of non-communicable illness and injury.¹⁴

Despite an increasing number of emergency physicians, most provinces outside of Port Moresby (the nation's capital) have under-developed primary and secondary care systems to facilitate emergency care.¹⁵ There is little data on the epidemiology of emergency presentations, and most EDs are not utilising triage scales. Triage has been identified as a priority for emergency care development for PICs, including PNG [personal communication, [name]].

Aims

The primary objective of this study is to measure the impact of a triage system on process indicators and clinical outcomes in a regional ED in PNG.

The secondary objective of this study is to determine the validity and reliability of the World Health Organization Triage Scale in this setting.

Methods

Setting

This study will be conducted in the ED of the Mount Hagen Provincial Hospital (MHPH) in the Western Highlands Province of PNG. The hospital is managed by the Western Highlands Provincial Health Authority (WHPHA).

Mount Hagen is the third largest city in PNG, with a population of approximately 50,000. It is the capital of the Western Highlands Province (population approximately 400,000), and a major administrative centre for the Highlands region.

MHPH is the city's major health facility. There is limited primary care infrastructure within the province, so patients rely on MHPH for the majority of their healthcare needs. As in other parts of the country, there is a large burden of both communicable and non-communicable disease, including HIV/AIDS, tuberculosis diabetes, cardiovascular disease, chronic respiratory conditions and trauma.

The ED receives approximately 150 presentations per day, and is staffed by one emergency physician, three registrars (specialists in training), five health extension officers (HEOs) and approximately thirty nurses. The ED has recently been redeveloped, and now includes four resuscitation bays, 16 acute beds and five short-stay beds. Basic pathology and radiology services are available.

Under current arrangements, the ED has no triage system and manual data collection processes are leading to gross under-reporting of presentation numbers. Major challenges for the ED include understaffing, a large burden of primary care patients and access block.

A new electronic database of ED patients has recently been implemented to capture basic attendance data. This system will facilitate data capture for the study.

Design

This study will utilise pre-post intervention methodology and will be prospectively registered as a clinical trial with the United States National Library of Medicine Clinical Trials Register at clinicaltrials.gov.

Pre-intervention

A new MHPH ED Patient Registration and Triage Form (PRTF) will be created to facilitate the new system and capture relevant data items, such as demographics and initial vital signs (Appendix 1). This form will be based on an existing MHPH ED discharge form, as well as a triage form successfully implemented in another Pacific setting.⁷

Data from the PRTF will be entered by ward clerks into the ED's electronic patient registration system (recently implemented as part of a hospital-wide data improvement project). This system forms part of the MHPH medical records database.

After a trial period of staff testing the new form, the PRTF will be implemented and baseline data captured in the database. During this period, the PRTF will not include any triage information (Appendix 1A). Based on a power calculation (see below), two months of pre-intervention data will be collected.

In order to identify patients who meet inclusion criteria, as defined below, the PRTF will require the treating clinician to indicate whether the patient had one of the ten sentinel conditions (listed below).

Intervention

The intervention will comprise implementation of a new triage and patient flow system facilitated through staff training and clinical redesign.

The three-tier World Health Organization Triage Scale (WHOTS) will be used as the triage instrument. This tool, developed collaboratively by the WHO, International Committee of the Red Cross (ICRC) and Médecins Sans Frontières (MSF), incorporates features of the SATS but has been modified for application in a wide variety of RL settings. WHOTS documents are provided in Appendix 2.

At the end of the baseline data collection period, MHPH ED staff will be trained in the new system. A variety of ED clinicians (who will subsequently take on the triage role) will be the focus of this training program. This will include nurses, community health workers and health extension officers in order to provide flexibility in the staffing model. Triage training will be delivered by an experienced Australasian volunteer nurse(s) and comprise workshops on triage principles, paper-based scenarios and simulation exercises.

Signage will be introduced to facilitate the new system of flow, and the ED will begin utilising the version of the PRTF that incorporates triage data (Appendix 1B). The triage instrument will be piloted over a one-month period (approximately). Modifications will be made based on real-time feedback as well as observations by the visiting team.

Post-intervention

After completion of the trial period, the new triage and flow system will be implemented under the leadership of local clinicians. The ED registration database will be updated to capture triage category data.

For admitted patients, hospital length-of-stay (LOS) and inpatient mortality data will be obtained from the WHPHA medical records database. These patients will be identified by the patient's unique hospital identification number.

Outcomes

Primary objective

The primary outcome will be time-to-assessment (TTA) by an ED clinician for ten time-critical conditions:

- Severe trauma
- Major burns
- Severe head injury
- Ruptured ectopic pregnancy
- Septic shock
- Myocardial infarction
- Severe asthma/COPD
- Severe pneumonia
- Meningitis
- Appendicitis

Pragmatic definitions for these conditions are provided at Appendix 3.

The primary outcome will also be analysed by the proportion of patients with these clinical syndromes that are seen within a clinically appropriate timeframe (defined as 15 minutes, as discussed below).

Secondary outcomes will include:

- Length of hospital stay
- ED mortality
- Inpatient mortality

These are also defined in Appendix 3.

Secondary objectives

Validity of the WHOTS will be assessed through its ability to predict ED outcomes. This will include the relationship between triage category and admission rates and ED mortality.

Under- or over-triage rates will also be calculated using disposition as a reference standard. This approach has limitations (see below) but is widely used in triage research.

Over-triage will be defined as the proportion of emergency (category 1) patients who are discharged. Under-triage will be defined as the proportion of non-urgent (category 3) patients who are admitted. Rates will be compared with the acceptable under- and over-triage rates recommended by ACS COT¹³ (and widely referenced in triage research) and then benchmarked against other published data. This approach has limitations (given that not all category 1 patients will require admission, and many category 3 patients could reasonably be expected to; recommendations for triage in trauma do not necessarily apply to other disease categories; and the performance targets provided by an American society do not necessarily apply to other contexts) but will be undertaken to enable comparison with other triage research from LMICs.

Reliability will be assessed through inter-rater agreement between two local triage nurses as well as a local nurse and independent expert triage nurse.

Analysis

All data will be obtained from the MHPH medical records database. Hospital medical records staff will export de-identified data into an Excel document, which will be provided to researchers and stored on a secure, password protected Monash University drive. All data will be analysed using Stata. No identifiable data will be available to the researchers.

Primary objectives

For the primary outcomes, Student's t-test will be used to compare the difference in TTA for the ten sentinel conditions (assuming parametric data). Chi-Square will be used to determine the difference in proportions of patients seen within 15 minutes.

For the secondary outcomes of ED mortality, hospital mortality and hospital LOS, Student's t-test or Chi-Square will be used as appropriate.

Secondary objectives

For predictive validity, Chi-Square and correlation coefficient derived by Cramer's V will be used to investigate the relationship between triage category and admission rates & ED mortality.

Under- and over-triage rates will be calculated using the definitions above. Acceptable limits set by the American College of Surgeons Committee on Trauma (an under-triage rate of less than 10% and an over-triage rate of 30–50%) will be used as the reference standard.¹³ This approach is consistent with that used in other triage research, despite the limitations discussed above.^{9–12}

For reliability, the modified Kappa statistic will be used to test inter-rater agreement between triage nurses.

Sample size

It is estimated that approximately 15 patients per day present with one of the ten sentinel syndromes and wait an average of 20 minutes to be seen. A clinically significant improvement in the TTA for these patients is thought to be five minutes. Although Australasian guidelines recommend that high acuity presentations (equivalent to categories one and two in the Australasian Triage Scale) are seen within 10 minutes of arrival,¹⁶ a target of 15 minutes is thought to be acceptable in the resource limited context of MHPH.

Based on these figures, a sample size of 34 (17 per group) will be required to demonstrate a clinically significant decrease in TTA for the selected time-critical conditions at an alpha of 0.05 and beta of 0.8.

The primary outcome will also be analysed by the proportion of patients seen within 15 minutes of arrival. Assuming baseline performance is 45%, an absolute improvement of 10% (to 55%) will require a sample size of 784 (392 per group) at an alpha of 0.05 and beta of 0.8.

The secondary outcome of mortality will require a larger sample. In order to demonstrate an absolute reduction in mortality of 5% (from an estimated baseline mortality rate of 15%), a sample size of 1372 (686 per group) is required at an alpha of 0.05 and beta of 0.8.

To ensure a satisfactory sample size to demonstrate all outcomes, pre- and post-intervention periods of 8 weeks will be utilised. This is based on a total sample size of 1372 for the secondary outcome of mortality (with a buffer of 10%) at an estimated presentation rate of 15 per day. This requires pre- and post-intervention periods of at least 50 days.

Ethics

Ethics approval, including a waiver of consent, will be sought from Monash University. Consistent with local processes, approval to conduct this research will then be sought from the Medical Research Advisory Committee within the Papua New Guinean National Department of Health.

Limitations

This study has been designed to ensure it is methodologically robust. There are, however, several limitations that will need to be considered when interpreting the results.

The pre-post nature of the design means that the study may be subject to confounding. A particular risk is that a new and efficient triage system may prompt an increase in ED presentations, and a change in the overall acuity of the patient cohort. For this reason, the primary outcome will focus on ten clearly-defined time critical conditions.

Other factors may also influence the primary outcome, such as changes in staffing levels and acute fluctuations in demand for emergency care (for instance, in the setting of disaster or outbreak). Within the influence of the researchers, attempts will be made to control these factors and minimise variation across the study period.

There is a risk that the study will be subject to the Hawthorne effect. Although treating clinicians will be blinded to the primary outcome, they will have knowledge of the ten sentinel conditions by virtue of their inclusion on the PTRF. It is therefore possible that patients presenting with these syndromes will be prioritised for care.

These limitations reflect the real-world challenges of conducting research in developing settings. The proposed study design is an attempt to balance methodological rigour with the practical considerations of emergency care delivery and research at MHPH.

Conclusion

Triage is an essential component of EC systems, especially in developing settings where demand for care typically exceeds the available resources. This study, using pre-post intervention methodology, will determine whether the introduction of a triage system leads to a clinically significant decrease in TTA for selected time-critical syndromes. It will also describe the impact on ED mortality, hospital mortality and total LOS.

A secondary objective of this study is to assess the validity and reliability of the WHO triage scale. There is currently no published data on the performance of this system.

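### The intervention is a triage-and-flow package, but its effect is described as that of triage, and waiting times of non-sentinel patients, which would help to interpret it, are not analysed

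*Combined protocol and SAP*

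**What the plan says.** **What is introduced.** The Intervention section defines the intervention as "a new triage and patient flow system facilitated through staff training and clinical redesign". On flow it adds: "Signage will be introduced to facilitate the new system of flow". The training consists of "workshops on triage principles, paper-based scenarios and simulation exercises". Under Post-intervention, "the new triage and flow system will be implemented under the leadership of local clinicians". Nothing is staggered: triage and flow start as one package in one ED.

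**What is to be concluded.** The Aims set out to "measure the impact of a triage system on process indicators and clinical outcomes". The Conclusion says that the study will determine "whether the introduction of a triage system leads to a clinically significant decrease in TTA", and its closing paragraph speaks simply of the impact of triage.

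**What is said of earlier work.** Of a paediatric ED study in Malawi, the background notes that although "training staff in emergency skills, introducing triage and improving flow, substantially reduced case fatality rates, the mortality reduction attributable to triage is unknown".

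**What is analysed.** Outcomes and Analysis confine TTA to the ten sentinel conditions: a t-test on the mean and a chi-square test on the proportion seen within 15 minutes, before versus after. No analysis of waits in other patients is planned. The Limitations cover presentation numbers and acuity, staffing, surges in demand and the Hawthorne effect, but not the bundling of triage with flow redesign.

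**The concern.** The design can estimate what happened to sentinel waits when the whole package arrived. It cannot say how much of that came from sorting patients by urgency. A department-wide fall in waits, whether from flow redesign, staffing or a time trend, and a fall confined to urgent patients produce the same pre-post difference in sentinel TTA. The background names this kind of attribution gap in earlier work, and the plan does not say that a similar gap remains here.

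Two things are at stake. EDs deciding what to adopt may credit the triage scale with a gain that needed the flow redesign as well. And if faster assessment of urgent patients lengthens the wait of the other nine in ten, the planned analysis will not show it.

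**Working it through.** **1. The plan's own figures.** None is disputed. The proportion calculation (45% to 55%, two-sided 0.05, 80% power, pooled variance) reproduces: [1.96 × √(2 × 0.5 × 0.5) + 0.8416 × √(0.45 × 0.55 + 0.55 × 0.45)]² / 0.10² = 391.3, so 392 per group. The 17 per group for a 5-minute difference in TTA comes without an SD; a t-test with SD 5 min gives 16.7, so 17.

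**2. Numbers available.** Setting gives about 150 presentations per day; Sample size gives about 15 sentinel patients per day and 8-week periods.
- Sentinel: 15 × 56 = 840 per period.
- Non-sentinel: (150 − 15) × 56 = 135 × 56 = 7,560 per period, 90% of presentations.

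**3. What each comparison estimates.** Write g for a change in wait common to all patients, p for the further change in sentinel patients, and q for the further change that triage causes in non-sentinel patients.
- Sentinel change (the planned test): g + p. The two parts cannot be separated.
- Non-sentinel change: g + q.
- Difference in changes: p − q. This removes g, but only if g really is equal in both groups, and it leaves q in.

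Two limiting illustrations, each with a 5-minute sentinel fall:

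| Mechanism | Sentinel change | Non-sentinel change | Difference |
|---|---|---|---|
| Equal speed-up for all | −5 | −5 | 0 |
| Re-ordering of a fixed queue | −5 | +5 × 15/135 = +0.56 | −5.56 |

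The planned test sees only the first column of results, which is the same in both rows.

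**4. Precision of the difference in changes.** With equal SDs and independent patients, SE = SD × √(2/840 + 2/7,560) = SD × 0.0514, and the 95% half-width is 1.96 × SE = 0.101 × SD.

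The SD is not stated, so a range is needed. SD 5 is what the 17 per group implies. The stated mean of 20 min with 45% seen within 15 min gives SD 14.3 under a lognormal shape and (20 − 15)/0.1257 = 39.8 under a normal shape. These figures describe sentinel patients; the plan gives none for the others.

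| Assumed SD (min) | 95% half-width (min) |
|---|---|
| 5 | 0.5 |
| 14 | 1.4 |
| 20 | 2.0 |
| 30 | 3.0 |
| 40 | 4.0 |

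If the non-sentinel SD is three times the sentinel SD, the multiplier becomes 1.96 × √(2/840 + 9 × 2/7,560) = 0.135, for example 2.7 min at a sentinel SD of 20. Correlation of waits within a day or shift widens all of these.

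**5. Precision of the non-sentinel change alone.** The half-width is 1.96 × SD × √(2/7,560): 0.6 min at SD 20, 1.9 at SD 60 and 2.9 at SD 90. A general 5-minute fall would be seen with 93% power even at SD 90. The 0.56-minute cost of pure re-ordering often would not: power is 40% at SD 20 and 8% at SD 60.

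**The case against.** The case on the other side has several parts.

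- **Wording.** The Intervention section defines the package openly, and a triage system can fairly be read as that package. The Conclusion is prospective and credits nothing yet. This softens the point. But the plan never states that reading, and its closing paragraph refers to triage alone.
- **Separability.** Sorting patients and routing them by category may not be meaningfully separable, and a pragmatic before-after study need not separate them. This stands, and it is a reason to name the package rather than to redesign the study.
- **Training.** A reader might infer that staff training is a further rival cause, exactly as in the Malawi study. The documents do not support that. The earlier study trained staff in emergency skills; the training here is in triage, so it is how triage is delivered. The parallel is close, not identical, and the open question is triage versus flow.
- **Staffing and demand.** The Limitations already name both and promise attempts to minimise variation. That is true, but no analysis would show a department-wide shift if those attempts fell short.
- **Not an untreated control.** A reader might infer that similar falls in both groups would prove a flow or staffing effect. That does not follow. Non-sentinel patients are also triaged and may include urgent cases outside the ten conditions, whose waits triage could shorten. Equally, flow redesign may favour urgent patients.
- **Feasibility.** The forms are not shown, and the Setting section reports gross under-reporting under manual data collection. The 7,560 per period may be optimistic, even with the new database.

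**Conclusion.** The point holds as an inexpensive improvement, not as a flaw that invalidates the primary analysis. The effect that the plan can estimate is that of the triage-and-flow package, plus anything else that changed between the periods. The Aims and Conclusion should say so. About 90% of presentations have no planned analysis of waiting time, although their change would help readers to interpret the sentinel result and would reveal a material cost to other patients.

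Two stronger readings should be resisted. First, no share of the targeted 5 minutes can be assigned to flow or to prioritisation, because the documents contain nothing from which to derive a split. Second, the comparison should not be presented as well powered for small differences: for a 2-minute difference in changes, power is about 49% at SD 20 and 16% at SD 40.

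The half-widths of 0.5 to 4.0 min rest on assumed equal SDs of 5 to 40 min, independent patients, the stated attendance rates, and times recorded for all patients. The last is an inference: the form is the ED registration form and carries a sentinel flag, which implies that it is completed for everyone.

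**What to change.** 1. Word the aim and conclusion as the effect of the combined triage and patient-flow package, and add bundling to the Limitations.
2. Prespecify a supportive analysis that reports the pre-post TTA change in non-sentinel patients next to the sentinel change, together with the period-by-sentinel difference and its 95% CI. Show both separate changes, not the difference alone, and allow for clustering by day or shift.
3. State beforehand that this analysis is supportive and does not isolate triage, and set no rule by which similar falls count as proof of a flow or staffing effect.
4. Confirm that arrival and first-assessment times are recorded for every patient in both periods. The sentinel flag can then define the groups throughout; triage category cannot, because it is absent from the pre-intervention form.

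The cost is some wording and one additional regression model. The sample size and the primary test are unchanged. The downside is a narrower claim and reliance on complete times for all patients.

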Appendix 1A – Pre-intervention Patient Registration and Triage Form

Appendix 1B – Post-intervention Patient Registration and Triage Form

See attached.

Appendix 2

World Health Organization Triage Scale – user guidance

See attached.

Appendix 3

Definitions for primary and secondary outcomes

Definitions related to primary outcomes

- Major trauma – any injury requiring blood transfusion or an intercostal catheter in the ED, or transfer direct to the operating theatre
- Severe head injury – any patient with objective evidence of a head injury and a Glasgow Coma Scale less than nine
- Major burns – any burn of greater than 15% total body surface area, as estimated by the treating clinician
- Myocardial infarction – an ECG positive for ST-elevation myocardial infarction, or raised troponin based on the threshold defined by the local laboratory
- Septic shock - fever (temperature $>37.5^{\circ}\text{C}$) and hypotension (systolic BP $\leq 90\text{mmHg}$)
- Ruptured ectopic pregnancy – objective evidence of pregnancy (extra-uterine gestational sac on ultrasound or positive urine βHCG) and free fluid on ultrasound
- Severe asthma/COPD – any patient with an oxygen requirement where the most likely diagnosis is an exacerbation of asthma or chronic obstructive pulmonary disease
- Severe pneumonia – any patient with an oxygen requirement where the most likely diagnosis is pneumonia
- Meningitis – any patient where the most likely clinical diagnosis is meningitis
- Appendicitis - any patient where the most likely clinical diagnosis is appendicitis

Time to assessment - the time interval in minutes between patient arrival at ED reception and the time of first assessment by the treating clinician

Definitions related to secondary outcomes

- Length of hospital stay – the number of days from presentation to discharge
- ED mortality – any death that occurs while the patient was physically in the ED, excluding patients who meet criteria for ‘deceased on arrival’
- Inpatient mortality - any death that occurs while the patient was admitted to hospitals, excluding any deaths that occur in the ED

Deceased on arrival is defined as any patient who is obviously deceased on arrival, as determined by the treating clinician.

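### Length of stay and inpatient mortality have no stated denominator, and data obtained for admitted patients invite a comparison that a change in admission could move in either direction

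*Combined protocol and SAP*

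**What the plan says.** The Post-intervention section gives the source of the ward data: "For admitted patients, hospital length-of-stay (LOS) and inpatient mortality data will be obtained from the WHPHA medical records database". No other passage plans the collection of stay data.

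Appendix 3 defines length of hospital stay as "the number of days from presentation to discharge". It does not limit this to admitted patients. It also does not say what value a patient discharged from the ED takes, or how a death ends the stay. Inpatient mortality is defined by its numerator only: deaths while admitted, with ED deaths left out.

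The Analysis section assigns an unadjusted t-test or chi-square test to ED mortality, hospital mortality and hospital stay, and names no analysis set. The Conclusion says "It will also describe the impact on ED mortality, hospital mortality and total LOS".

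The Sample size section starts from the estimate that "approximately 15 patients per day present with one of the ten sentinel syndromes" and states for mortality that "a sample size of 1372 (686 per group) is required at an alpha of 0.05 and beta of 0.8". It does not say whether this is ED, inpatient or combined mortality.

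Admission rates appear only in the validity analysis, by triage category. No passage compares the admission proportion before and after the intervention.

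**The concern.** Admission is decided after the patient has passed through the new triage and flow system. The intervention redesigns flow in a department that the protocol describes as having access block, so the mix of patients admitted may differ between periods. A before-after comparison within admitted patients then conditions on an event that the intervention may influence. The Limitations section restricts attention to ten conditions to guard against changed presentations and acuity. That does not help here, because the selection would act within those ten conditions.

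Mean stay and inpatient mortality among admitted patients could therefore worsen or improve while every patient fares the same. With the denominator unstated, the choice between the two populations also stays open until after the data are seen. Mortality is a secondary outcome, but it sets the length of the study periods.

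**Working it through.** **The plan's own figure.** Inputs from the Sample size section: 15% against 10%, alpha 0.05, the stated beta of 0.8 read as power of 0.80, equal groups. The two-sided pooled-variance formula without continuity correction gives 686 per group, which matches. With the 10% buffer, 686 × 1.10 / 15 = 50.3 days, which matches the stated minimum of about 50 days. Eight weeks give 56 × 15 = 840 sentinel patients per period.

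**Power if mortality were analysed in admitted patients only.** The admission share is not in the documents, so it is varied. The number per period is 840 × share, tested at 15% against 10%.

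| Share admitted | n per period | Power |
|---|---|---|
| 100% (same as all sentinel patients) | 840 | 0.87 |
| 90% | 756 | 0.84 |
| 80% | 672 | 0.79 |
| 70% | 588 | 0.74 |
| 60% | 504 | 0.67 |
| 50% | 420 | 0.59 |

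Eight weeks supply 686 admitted patients per period only if at least 686 / 840 = 81.7% are admitted.

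**Effect of a change in admission alone.** Assumptions, none from the documents except the 840:

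- 80% admitted before the intervention, so 672 patients
- mean admitted stay 6 days, SD 6
- 15% of those admitted die, so 100.8 expected deaths
- patients whose admission status changes would stay 1 day if admitted and do not die
- patients not admitted count 0 days

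For a post-intervention share *a*:

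- admitted-only stay = (0.80 × 6 − (0.80 − a) × 1) / a
- all-sentinel stay = 4.8 − (0.80 − a) × 1
- admitted-only mortality = 100.8 / (840 × a)
- all-sentinel inpatient mortality = 100.8 / 840 = 12.0% throughout

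| Share admitted after | Admitted-only stay (6.0 before) | All-sentinel stay (4.8 before) | Admitted-only mortality (15.0% before) | All-sentinel inpatient mortality (12.0% before) |
|---|---|---|---|---|
| 75% | 6.33 | 4.75 | 16.0% | 12.0% |
| 70% | 6.71 | 4.70 | 17.1% | 12.0% |
| 90% | 5.44 | 4.90 | 13.3% | 12.0% |

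At 70% the difference in stay is 0.71 days with SE 6 × √(1/672 + 1/588) = 0.34. A significant rise would then appear in about 56% of studies. At 75% the difference is 0.33 days, SE 0.33, and the chance is about 17%. For mortality at 70%, SE = √(0.15 × 0.85/672 + 0.171 × 0.829/588) = 0.021, so z = 0.021 / 0.021 ≈ 1.0 and the chance of a significant rise is about 18%.

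Over a wider set (start at 80% or 90% admitted, fall of 5 to 15 points, low-risk stays of 1 to 3 days), admitted-only mortality ends between 15.9% and 18.5%, and stay between 6.2 and 7.2 days.

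**Masking of a real benefit.** Suppose deaths truly fall from 15% to 10% of the original 672, to 67.2, while admission falls to 70%. Admitted-only mortality after the intervention is 67.2 / 588 = 11.4%, and power falls to about 0.46. Over all sentinel patients the same data read 12.0% against 8.0%, with power about 0.78.

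**The case against.** The sentence in the Post-intervention section names a data source, not an analysis set. Ward data exist only for admitted patients, so it does not say who enters the comparison. Under Appendix 3 a patient never admitted cannot be an inpatient death, so an all-sentinel inpatient mortality rate can already be computed from the planned data. Sizing mortality on all sentinel presentations fits that denominator. This stands: for mortality the gap is an unstated denominator, not a demonstrated error. A reader might infer from the sizing that the study is underpowered for mortality, but the documents do not say that the analysis is restricted to admissions, or which mortality the 15% refers to.

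A reader might also take total stay in the Conclusion as a promise to measure stay in every sentinel patient. The term is undefined and may mean ED plus ward time, so it does not establish a contradiction.

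A third tempting inference is that the intervention will lengthen stay and raise mortality. The documents describe no changed admission criteria, and the table shows that rising admission moves both measures the other way.

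Finally, most of the ten conditions are defined by severity, for example shock, a low coma score or an oxygen requirement. Few such patients may be sent home, and the 80% to 70% scenario means 84 fewer admissions per period. This also stands as a limit on size, but the documents give no admission figure to settle it.

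These arguments do not answer the point about length of stay. Stay data are planned for admitted patients, no rule covers the others or those who die, and no comparison of admission between periods would reveal a shift.

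**Conclusion.** The point holds as a gap in specification with a real risk of bias. It is stronger for length of stay, where the plan leads naturally to an admitted-only t-test. For inpatient mortality it is conditional on dividing by admissions, which the plan neither states nor excludes.

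The direction of any bias is not determined, and its size cannot be derived from the documents. The figures above rest on assumed admission share, stay, SD, death rate and low-risk stay. They show that a shift of 10 percentage points in admission could move mean stay by more than half a day and mortality by about 2 points with no change in outcome. If nearly all sentinel patients are admitted in both periods, the effect is small. The 686 per group is correct for its stated inputs and is not in question. The change should be made, because it removes the risk at almost no cost.

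**What to change.** Amend the Post-intervention and Analysis sections and Appendix 3 as follows.

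- **Mortality.** Use all sentinel patients not deceased on arrival as the denominator. Report ED plus inpatient deaths combined alongside the two separate outcomes. Appendix 3 splits deaths by location, so a shift in where patients die would otherwise move inpatient mortality even over all sentinel patients.
- **Length of stay.** Compare days from presentation to discharge over the same patients. Those discharged from the ED contribute their actual days, 0 if the same day. State how deaths in the ED and on the ward enter the measure, since a stay shortened by death is not a benefit.
- **Supporting results.** Report the admission proportion in each period, and the admitted-only stay and mortality beside it.

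The cost is a few sentences and a little extra analysis. Disposition is already needed for the admission and mis-triage analyses. The sponsor should confirm that the date of ED discharge is also recorded, because the forms are not reproduced in the text. The small downside is more zeros in length of stay and a less familiar headline figure, which the admitted-only results offset.
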